1.4 Justification for Dose Selection

Benefit/Risk Assessment:

The doses administered in the Phase 2b and Intermediate Parts of Study AV-101-002 are 10 mg, 35 mg, and 70 mg BID. In the LTE study, subjects will continue on the same active dose and placebo subjects will be re-randomized to one of these active doses until such time as the optimal dose has been selected from the Phase 2b data based upon efficacy, safety, and tolerability. Once the optimal dose has been selected, subjects in the LTE will be transitioned to the optimal dose. Subjects on the optimal dose or placebo in the Phase 3 Part of AV-101-002 will continue in the LTE at the optimal dose.

2 Objectives and Endpoints

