The Week 24 end of study visit of the parent study (AV-101-002) also represents the baseline visit for the LTE study (AV-101-003). The following assessments will be conducted/collected during the baseline visit of the LTE and at selected time points specified in the Schedule of Assessments (Table 1). Additional procedures deemed necessary as part of standard of care may be performed at the discretion of the Investigator. All missed visits and any performed procedures that are not protocol-specified activities must be documented in the subject's medical record and the appropriate eCRF. General considerations for study visits include, but are not limited to the following:

- No protocol waivers or exemptions are allowed.
- Immediate safety concerns should be discussed with the CRO Medical Monitor immediately upon occurrence or awareness to determine if the subject should continue or discontinue study drug.
- Adherence to the study design requirements, including those specified in the Schedule of Assessments, is essential and required for study conduct (see Section 6.7.1 for COVID-19 considerations).
- The Investigator will obtain written informed consent before the end of study visit for study AV-101-002 and as specified in Section 9.1.3 (Informed Consent Process). Upon the subject's agreement, their primary health care provider should be informed about the subject's enrollment in the study.
- Order of Procedures:
 - Health-related QoL assessments should be performed prior to all other study procedures.
 - Vital signs should be collected prior to blood draws. Blood samples for NT-proBNP levels should be collected prior to the 6MWT.
 - All other study assessments should also be performed, according to the Schedule of Assessments (Table 1).
- **Unscheduled visits:** may occur at any time during the study with the assessments to be performed according to the Investigator's judgment. Unscheduled visits may also be necessary for study drug dispensing following temporary withdrawal as described in Sections 6.7 and 7.7.

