8.1 Introduction: Study Design and Analysis Overview

The LTE is a longitudinal study of the long-term safety and effectiveness of PAH patients treated with AV-101 at different dose levels until being transitioned to the optimal dose of AV-101 which is selected after the completion of the Phase 2b Part of Study AV-101-002 (referred to as the parent study). About 370 subjects (with a maximum of 462 subjects) are expected to start the LTE. LTE subjects may be grouped into the following treatment groups:

- **Group 1 – Optimal Dose Treatment:** Subjects treated with the optimal dose throughout the parent trial and throughout their LTE participation.
- **Group 2 – Non-Optimal Dose Active Treatment, then Optimal Dose Treatment:** Subjects treated with active doses not selected as the optimal dose, who eventually will be treated with the optimal dose when this dose is selected.
- **Group 3 – Placebo to Non-Optimal Dose, then Optimal Dose Treatment:** Subjects originally assigned to the placebo arm during the parent trial then re-randomized to the two non-optimal active groups. Later, they will receive the optimal dose when it is selected.
- **Group 4 – Placebo to Optimal Dose Treatment:** Subjects originally assigned to the placebo arm during the parent trial then either re-randomized or switched to optimal dose.

Further characteristics of these LTE treatment groups are described in [Section 8.3](#).

Among the comparisons to consider are:

- 1) LTE levels and trends among subjects always on the optimal dose Group 1 will be compared in order with those of:
 - Group 4: Placebo to optimal dose treatment
 - Group 3: Placebo to non-optimal dose, then optimal dose treatment
 - Group 2: Non-optimal dose active treatment, then optimal dose treatment
- 2) Levels and trends in LTE safety and effectiveness endpoints for subjects always on the optimal dose (Group 1) will be compared to levels and trends during the parent study among these same subjects. This will be done to document whether the effects of the previous optimal dose on subsequent measures of effectiveness and safety while still undergoing treatment persist, improve, plateau, or dip the longer the duration of the optimal treatment.
- 3) Trends in continuous LTE effectiveness endpoints will be assessed separately for continuous dose intensity and continuous relative dose intensity.

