Visits within a subject form a cluster. Estimated proportions by treatment group and visit will be reported. For Week 24 after optimal dose treatment, the log of odds and proportions of subjects who maintain or improve WHO FC and their 95%CI will be reported by treatment groups. Odd ratios (OR) and 95%CI for subjects always on optimal dose (Group 1) relative to those subjects on always on placebo (Group 4) will be reported. OR and 95%CI among subjects always on optimal dose (Group 1) relative to those of subjects on placebo and then active treatment (Group 3) and OR and 95%CI among subjects always on optimal dose (Group 1) relative to those of subjects on non-optimal dose (Group 2) will also be reported.

4) Time to Clinical Worsening

Time to clinical worsening while in the parent trial and LTE will be based on the first occurrence of any of the following events for each subject.

- Death
- Initiation of parenteral prostanoids
- Hospitalization for worsening PAH
- $\geq 15\%$ decline from baseline in 6MWD and accompanied with progression to or continued WHO FC III or IV symptoms

A subject is evaluated for experiencing any of the above components of clinical worsening throughout the parent trial and LTE study period. Time to clinical worsening is the number of days between the earliest occurrence of the clinical worsening component and the date of the first dose in the parent trial. With treatment groups that change over time intervals, event and censoring will be defined within each time interval. A subject who does not experience any of the clinical worsening component throughout a treatment period/interval is censored and is assigned time to worsening status by the end of the interval. Subjects who are lost to follow-up are typically considered censored. Supplemental analyses will be performed where subjects with an unknown clinical worsening event will be considered to

experience the event and the time to clinical worsening status is the last contact with the subject.

The probability of clinical worsening every 24 weeks after the first dose in the parent trial throughout the LTE will be reported, descriptively as well as based on a Cox model for time to clinical worsening while holding covariates at their means.

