A Cox model will be fitted to time to clinical worsening with terms for time-varying by treatment dose groups, continuous LTE baseline REVEAL Lite 2.0 score (among those randomized to placebo in Phase 3), continuous parent baseline REVEAL Lite 2.0 score, and IPAH/HPAH or Non-IPAH/HPAH category.

The hazard ratio and its 95% CI for the pairwise treatment dose groups will be reported for:

- Always on the optimal dose (Group 1) versus always on placebo (Group 4)
- Always on the optimal dose (Group 1) versus on placebo followed by an active dose (Group 3)
- Always on the optimal dose (Group 1) versus always on a non-optimal dose (Group 2)

Kaplan-Meier curves by parent trial treatment groups will be generated.

5) Achieving multicomponent clinical improvement will be analyzed as a binary as well as a time to event response throughout the LTE period

a) Binary response throughout LTE period: At each LTE visit, a subject response is set to 1 for achieving multicomponent clinical improvement if he meets all of the following three conditions:

- FC improvement or maintenance of FC II status
- NT-proBNP \geq 30% improvement or $<$ 300 pg/ml
- 6MWD \geq 30 meters improvement

Otherwise, the response value is 0.

A logistic regression model will be fitted to the binary response of achieving multicomponent clinical improvement at each visit. The explanatory variables will include LTE treatment groups categorical visit, LTE treatment groups by visit interaction, continuous LTE baseline REVEAL Lite 2.0 score, continuous parent baseline REVEAL Lite 2.0 score, and IPAH/HPAH or Non-IPAH/HPAH category. The subject's multicomponent clinical improvement status during the parent study may be considered as an explanatory variable. Subjects will be specified as clusters.

b) **Time to Event Response from start to end of the LTE:** Time to achieve multicomponent clinical improvement response is defined as the days since the first

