dose that a subject achieves clinical improvement in all 3 components from the start through the end of LTE. The number of days between the date that a subject meets all of the multicomponent improvement parameters and the first LTE dose date is the time to achieving multicomponent improvement. A subject who does not experience multicomponent improvement is censored during the time interval. A subject who is lost to follow-up without recording this multicomponent improvement is censored at the last visit in which the above parameters are recorded. Supplemental analyses will be performed where those lost to follow-up are considered a failure at the time of the lost to follow-up.

The Cox hazard model as described for time to clinical worsening will be implemented for time to multicomponent clinical improvement.

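### The clinical-worsening Cox model limits its LTE-baseline REVEAL term to Phase 3 placebo subjects, gives no coding for anyone else, and measures it 24 weeks after time zero

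*Combined protocol and SAP*

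**What the plan says.** Section 8.5.2 (4) analyses time to first clinical worsening over the parent trial and the LTE. Time is the number of days between the "earliest occurrence of the clinical worsening component and the date of the first dose in the parent trial".

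The model is introduced as follows: "A Cox model will be fitted to time to clinical worsening with terms for time-varying by treatment dose groups". Its other terms are the parent-baseline REVEAL Lite 2 score, IPAH/HPAH category, and "continuous LTE baseline REVEAL Lite 2.0 score (among those randomized to placebo in Phase 3". For subjects outside that parenthesis the text gives no value, indicator, interaction or centring. Hazard ratios are planned for Group 1 against Groups 4, 3 and 2; the first is listed as "Always on the optimal dose (Group 1) versus always on placebo (Group 4".

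Other places that bear on the term:

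- Section 8.1 defines Group 4: "Subjects originally assigned to the placebo arm during the parent trial then either re-randomized or switched to optimal dose".
- Section 1.4: "Subjects on the optimal dose or placebo in the Phase 3 Part of AV-101-002 will continue in the LTE at the optimal dose".
- Section 6: "The Week 24 end of study visit of the parent study (AV-101-002) also represents the baseline visit for the LTE study (AV-101-003".
- Table 1 schedules the REVEAL Lite 2 score at Screening/Baseline for every LTE subject.
- The WHO Functional Class model in 8.5.2 (3) and the logistic model in 8.5.2 (5a) both use the LTE-baseline score without restriction.
- Section 8.5.2 (5b): "The Cox hazard model as described for time to clinical worsening will be implemented for time to multicomponent clinical improvement".

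**The concern.** A covariate defined only inside part of one comparison group cannot enter an all-group model until someone decides what the other subjects carry. The plan leaves that open, and the obvious choices give different answers for a first-tier endpoint. The LTE is unblinded once the optimal dose is chosen (Section 3.1, note C), so the choice could be made with treatment known.

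There is also a timing problem. The clock starts at the first parent dose, but the score is taken at parent Week 24. LTE entrants were alive at Week 24, but a hospitalization, a start of parenteral prostanoids or a confirmed walk-distance decline before then would count as an event. As a fixed covariate, the score would then have been measured after the event that it is meant to explain.

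**Working it through.** **Who carries the term.** Phase 3 placebo subjects all go to the optimal dose on LTE entry (Section 1.4), so all are in Group 4 (Section 8.1). None is in Groups 1 to 3. Group 4 may also hold Phase 2b and Intermediate placebo subjects re-randomized to what became the optimal dose.

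**Coding A: missing for everyone else.** A complete-case fit keeps only Phase 3 placebo subjects. Group 1 is absent, so none of the three hazard ratios can be estimated.

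**Coding B: 0 for everyone else, uncentred.** First the scale. From Table 3 the lowest total is 6 - 1 (FC I) - 2 (6MWD) - 2 (NT-proBNP) = 1, which matches the stated lower end of the low-risk category. The highest is 6 + 1 + 2 + 1 + 1 + 1 + 2 = 14. Zero is off the scale.

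Let γ be the Group 4 coefficient and β the coefficient of the restricted score. If Group 4 is all Phase 3 placebo, the Group 1 versus 4 hazard ratio at score s is HR(s) = exp(-γ - βs). The reported group coefficient gives HR(0) = HR(m) × exp(βm), where m is the subgroup mean. The factor exp(βm) is:

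- 1.1 per point, mean 6: 1.1^6 = 1.77
- 1.2 per point, mean 6: 1.2^6 = 2.99
- 1.3 per point, mean 7: 1.3^7 = 6.27

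The documents give no group sizes, event rate or REVEAL effect for this model, so the simulation inputs are assumptions: 150 Group 1 and 100 Group 4 subjects; scores with mean about 6.5 and SD 2; parent-score log hazard 0.05 per point; LTE-score log hazard 0.1, 0.2 or 0.3 per point; group fixed over time; 200 replicates per setting. Results for a true Group 1 versus 4 hazard ratio of 0.70:

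| Group 4: Phase 3 / earlier placebo | Zero-coded HR at 0.1, 0.2, 0.3 | SD of log HR | HR with term deleted | SD of log HR |
|---|---|---|---|---|
| 100 / 0 | 1.03, 1.51, 2.54 | 0.52-0.60 | 0.71, 0.68, 0.72 | 0.17-0.20 |
| 80 / 20 | 0.74, 0.85, 0.98 | 0.31-0.33 | 0.69, 0.70, 0.72 | 0.18-0.19 |
| 50 / 50 | 0.74, 0.75, 0.79 | 0.24-0.25 | 0.71, 0.71, 0.72 | 0.19-0.20 |

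The first row agrees with the formula. The fitted β is smaller than the generating value (0.054, 0.112, 0.176) because the parent score absorbs part of the effect. With the centred hazard ratios 0.73, 0.73 and 0.81 as HR(m):

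- 0.73 × exp(0.054 × 6.5) = 1.04
- 0.73 × exp(0.112 × 6.5) = 1.51
- 0.81 × exp(0.176 × 6.5) = 2.54

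With a true hazard ratio of 1.0, zero-coding gives 1.41, 2.16 and 3.27 (all Phase 3), 1.13 to 1.29 (80/20) and 1.01 to 1.08 (50/50). Deleting the term gives 0.98 to 1.01.

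**Groups 2 and 3 under coding B.** Groups 1, 2 and 3 all carry 0, so the term can reach their contrasts only through small shifts in shared coefficients. A four-group simulation (assumed sizes 120/120/60/100, with 70 of Group 4 from Phase 3) gave Group 1 versus 2 at 0.79-0.84 with the term and 0.80-0.84 without, and Group 1 versus 3 at 0.72-0.75 in both, with unchanged standard errors. In the same setting Group 1 versus 4 was 0.69-0.81 and its standard error rose about 1.4-fold.

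**Coding C: centred at the Phase 3 placebo mean, 0 for others.** This gives 0.70-0.81 for a true 0.70 and 1.00-1.13 for a true 1.0. Most of the distortion goes, but the plan does not specify this coding.

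**Timing.** In (4) time zero is the first parent dose and the score comes at Week 24. In (5b) time zero is the first LTE dose and the LTE-baseline score precedes it.

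**The case against.** Section 8 calls itself an overview and defers details to an SAP, and the study's objective is long-term safety and tolerability. On that view this is one loosely worded covariate in one of several effectiveness models. The values are collected for everyone, so a programmer would lose Groups 1 to 3 only by blanking data already held. The score could enter from LTE start as a time-updated term. The parenthesis might be shorthand for one baseline per subject, in line with Sections 8.1 and 8.4.

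Some of this stands. A reader might infer that the score does not exist outside Phase 3 placebo; Table 1 shows that it does, and the restriction is on the model term alone. A reader might also infer that missing and zero are the only two codings; centring is a third.

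The rest does not rescue the wording. The restriction is stated, and it departs from the unrestricted use in (3) and (5a), so it is more than missing detail. The one-baseline reading does not fit: parent-baseline REVEAL is listed as a separate term, and naming Phase 3 leaves out Phase 2b and Intermediate placebo subjects. The time-varying covariates in Section 8.1 are specified as dose intensity, and nothing says that REVEAL enters at LTE start. Holding covariates at their means is stated in (4) for predicted probabilities, not for hazard ratios.

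**Conclusion.** The point holds. As written, the restricted term either leaves no pairwise hazard ratio estimable (complete-case) or, under uncentred zero-coding, distorts the Group 1 versus Group 4 hazard ratio and widens its interval. As a fixed covariate it also post-dates any event in Weeks 0 to 24.

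The size rests on assumed group sizes, score distribution and log hazard per point, with group held fixed over time. For a true hazard ratio of 0.70, zero-coding gives about 0.7 to 1.0 when Group 4 is mixed and about 1.0 to 2.5 when it is all Phase 3 placebo. In the all-Phase-3 case the apparent direction can reverse. The plan does not give the mix, so neither range is a prediction.

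Three stronger readings are not supported. A reader might infer that all three hazard ratios are biased under any coding; under zero-coding, Group 1 versus 2 and 1 versus 3 are essentially untouched. A reader might take a contrast purely at score 0 as certain; it requires Group 4 to be entirely Phase 3 placebo, and Section 8.1 admits earlier placebo subjects. A reader might carry the timing argument into (5b); the clock there starts at the first LTE dose, so only the missing coding carries over.

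**What to change.** - In 8.5.2 (4), delete the LTE-baseline REVEAL term from the Cox model. Keep parent-baseline REVEAL Lite 2 and IPAH/HPAH category for all subjects. Simply entering the LTE-baseline score for everyone would leave the timing problem, and for Groups 1 and 2 it would adjust for a value taken after 24 weeks of AV-101.
- If an updated risk score is wanted, add a supportive model with REVEAL Lite 2 time-updated for every subject, each value entering from its measurement date.
- In 8.5.2 (5b), state the covariates explicitly instead of by reference, and drop the Phase 3 placebo restriction so that the LTE-baseline score enters for all subjects, as in (5a).

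The cost is a line of wording in each place. No new data, visits or subjects are needed. The change should be made before the hazard ratios are run.

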- Hospitalization for worsening PAH
- Initiation of parenteral prostanoids
- $\geq 15\%$ decline from baseline in 6MWD accompanied with continued or worsening WHO FC III or IV symptoms. The decline in 6MWD must be confirmed with a repeat test on a different day within 2 weeks. (Baseline is defined by the randomization visit in Study AV-101-002 for those on AV-101 and the Week 24 visit for those on placebo in Study AV-101-002).

Clinical Improvement from baseline will be assessed by the proportion of subjects achieving all 3 of the following components at 6 month intervals:

- WHO FC improvement or maintenance of WHO FC II status
- NT-proBNP $\geq 30\%$ improvement or < 300 pg/ml
- 6MWD ≥ 30 -meter improvement

The change from baseline in the REVEAL Lite 2.0 risk score ([Benza, 2020](#)) at 6 month intervals classified as low, intermediate, or high risk will be assessed using the following variables to derive the risk score:

- Estimated Glomerular Filtration Rate (eGFR) in ml/min/1.73 m² or renal insufficiency if GFR is unavailable
- WHO FC

- Systolic blood pressure and heart rate
- 6MWD
- NT-proBNP

Transthoracic Echocardiogram will be assessed and evaluated at 6 month intervals.

Safety and tolerability of AV-101 will be assessed using the following:

- Adverse Events
- Pulmonary Function Tests at 24-week intervals (Spirometry including FEV₁ and FVC, peripheral oxygen saturations and DLCO [Diffusing Capacity of the Lungs for Carbon Monoxide])
- Safety Laboratory Tests at Weeks 4 and 12, and at 12-week intervals thereafter (including chemistry and complete blood count)

Adverse events will be collected throughout the study period.

Safety data analyses

The independent DSMB will monitor safety at regular intervals throughout the Phase 2b/3 study as well as during the LTE study. Details regarding the members, meeting frequency and stopping rules will be specified in the DSMB charter.

Blinding and unblinding considerations

The study will remain blinded until the optimal dose from Study AV-101-002 has been identified. In the event of a medical emergency, the Investigator will be able to receive the treatment assignment, if required to provide optimal care of the subject. Instructions for Emergency Unblinding can be found in the IWRS Manual. See also [Section 7.6](#) Procedures for Breaking the Treatment Code.

Compliance

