6.6.4 WHO Functional Class

WHO FC will be assessed at all study visits.

Class Description

- | | |
|------------|--|
| Class I: | Pulmonary hypertension but without resulting limitation of physical activity. Ordinary physical activity does not cause undue dyspnea or fatigue, chest pain or near syncope. |
| Class II: | Pulmonary hypertension resulting in slight limitation of physical activity. Subject is comfortable at rest. Ordinary physical activity causes undue dyspnea or fatigue, chest pain or near syncope. |
| Class III: | Pulmonary hypertension resulting in marked limitation of physical activity. Subject is comfortable at rest. Less than ordinary physical activity causes undue dyspnea or fatigue, chest pain or near syncope. |
| Class IV: | Pulmonary hypertension with inability to carry out physical activity without symptoms. Subject manifests signs of right heart failure. Dyspnea and/or fatigue may even be present at rest. Discomfort is increased by any physical activity. |

The Investigator will complete the WHO Functional Class assessment. Every effort should be made to have the same Investigator or medically qualified designee assess the subject at each study visit.

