6.6.6 Clinical Improvement

Clinical improvement will be assessed by the proportion of subjects achieving all 3 of the following components at 6 month intervals:

- WHO FC improvement or maintenance of WHO FC II status
- NT-proBNP $\geq 30\%$ improvement or < 300 pg/ml
- 6MWD ≥ 30 -meter improvement

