8.4 Baseline and Demographics and Subject Study Disposition

With exception of the delayed-start analysis, for both the efficacy and safety analyses, baseline will be defined as the time prior to starting active treatment with AV-101 in either the LTE or the parent study. For Groups 1 and 2, since the subjects start receiving active treatment in the parent study, the baseline will be the values prior to first dose during the parent trial. For Groups 3 and 4, the subjects receive placebo in the parent trial and then receive active treatment in the LTE study, thus, the baseline will be the values prior to the first dose in LTE study.

Demographics and baseline data, medical and surgical history will be summarized using the screened analysis set. These demographics and baseline data will be presented by the LTE treatment groups as described in [Section 8.1](#).

Demographic and baseline data will be summarized using summary statistics of mean, standard deviation, median, lower quartile, upper quartile, min and max for continuous variables and number and percentage of subjects in each category.

Subject treatment status and study participation status will be reported for the safety analysis set. Subjects who completed all LTE assessments and early treatment discontinuation and withdrawal from the study including reasons for treatment or study discontinuation will be reported by LTE treatment groups.

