Unstructured covariance will be specified. If the fitted model does not converge with unstructured covariance, a simpler covariance will be specified. LSMeans by trial treatment groups and difference in mean change from baseline in NT-proBNP at each visit will be reported. At each post-baseline visit (with focus on Weeks 24, 48 and 72 after LTE entry) the difference in mean change from baseline in NT-proBNP between treatment groups and its 95% CI for the treatment term will be reported. The mean difference in change from LTE baseline between subjects always on the optimal dose will be compared in the following order: 1) always on placebo (Group 4); 2) placebo followed by an active treatment dose (Group 3); 3) always on the non-optimal dose (Group 2). Average treatment effectiveness before and after optimal dose treatment during the LTE will also be presented.

Trends in change from baseline (CFB) will initially be assessed graphically. To obtain a measure of trends using MMRM, visits as continuous variables, and visit by LTE treatment groups interactions will be entered into the model. The coefficient for continuous visit associated for each of the LTE treatment groups indicates the linear trend in change from baseline over visit. A non-linear trend in CFB will be tested by entering visit as quadratic or cubic spline of visit in the model.

3) Maintenance or improvement in WHO Functional Class throughout the LTE

At each post-LTE baseline visit, a subject's status with respect to remaining in or decreasing from the same WHO FC will be recorded. At each post-baseline visit, the proportion of subjects who remain or improve on their baseline WHO FC will be reported by treatment groups. A logistic regression model will be fitted where the response at each visit is whether the subject remains in or improves in WHO FC. The explanatory variables consist of LTE treatment groups, visit, LTE treatment groups by visit, IPA/HPA or non-IPA/HPA category, and continuous LTE baseline REVEAL Lite 2.0 score.

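### The functional-class component of clinical improvement gives no credit for staying in WHO FC I, so a subject in FC I at the reference baseline can never be a responder, and 8.5.2(5) does not say which baseline applies

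*Combined protocol and SAP*

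**What the plan says.** The rule appears in the synopsis, 2.2, 6.6.6 and 8.5.2(5a), with the same content each time. Section 6.6.6 words the functional-class component as "WHO FC improvement or maintenance of WHO FC II status", and 8.5.2(5a) as "FC improvement or maintenance of FC II status". The other two components are NT-proBNP (improved by at least 30%, or below 300 pg/ml) and 6MWD (a gain of at least 30 m). Section 8.5.2(5a) scores a subject 1 for "achieving multicomponent clinical improvement if he meets all of the following three conditions", and then adds "Otherwise, the response value is 0". The synopsis makes the comparison relative to baseline: "Clinical Improvement from baseline will be assessed by the proportion of subjects achieving all 3 of the following components". Item 5(b) uses the same three components for time to improvement and censors subjects who do not reach them.

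FC I is the best class in 6.6.4: "Pulmonary hypertension but without resulting limitation of physical activity". Sections 4.1 and 4.2 set no functional-class limit for LTE entry, and Table 3 (REVEAL Lite 2) assigns FC I its own score.

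Section 8.4 sets the baseline for all efficacy and safety analyses except the delayed-start analysis. For Groups 1 and 2 it is the parent-study value before first dose. Groups 3 and 4 received placebo in the parent study, "thus, the baseline will be the values prior to the first dose in LTE study". The synopsis and 8.1 agree. Section 8.5.2(5) itself names no baseline for the components.

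**The concern.** The component suits a population that starts in FC II or worse. It credits holding FC II but not holding the better class. Nothing in the documents gives a reason for this, and the rest of the plan leans the other way. The NT-proBNP component accepts an already good value. Item 3 of 8.5.2 counts as success "whether the subject remains in or improves in WHO FC", so a stable FC I subject succeeds there and fails here.

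Two things are at stake. At subject level, someone in the best class who meets both other components is recorded as a non-responder because of the wording. At group level, the composite is a first-tier endpoint, and 8.5 compares Group 1 with Groups 4, 3 and 2. If the share in FC I at the reference baseline differs between groups, the odds and hazard ratios pick up a difference that comes from the definition and not from treatment.

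**Working it through.** **Step 1: enumerate the rule.** Taken literally, and judged against baseline, the component is met if visit FC is better than baseline FC, or if both are FC II. Across the 16 pairs of baseline and visit class:

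| Baseline FC | Visit classes that qualify as written | If holding FC I is also credited | Item 3 (remain or improve) |
|---|---|---|---|
| I | none | I | I |
| II | I, II | I, II | I, II |
| III | I, II | I, II | I, II, III |
| IV | I, II, III | I, II, III | I, II, III, IV |

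Only the FC I row is empty. The response is 0 at every visit for such a subject, whatever the other two components show. If f is the share of a group in FC I at the reference baseline, the group's response rate cannot exceed 1 − f.

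**Step 2: see which groups are affected under each baseline.** Take two subjects who are both in FC I at LTE entry and stay there. One was on active drug and began the parent study in FC II; the other was on placebo.

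- *Split baseline of 8.4.* The ex-active subject is compared with FC II at parent entry and meets the component. The ex-placebo subject is compared with FC I at LTE entry and never can. The loss falls on Groups 3 and 4, provided nobody in Groups 1 and 2 was in FC I at parent entry.
- *LTE baseline for all groups.* Both subjects are compared with FC I, and both are locked out. The net direction then depends on which group has more subjects in FC I at LTE entry. If more reached FC I on drug, Group 1 loses more.

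**Step 3: size under the 8.4 baseline.** The documents give no response rate and no FC I share, so there is no planned figure to reproduce. All three inputs are assumptions:

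- f: share of an ex-placebo group in FC I at baseline, 2% to 10%;
- p: response rate among its other subjects, 20% to 30%;
- r: response of FC I subjects relative to p, if they were credited, 0.5 to 1.

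Rate as written = (1 − f)p. Rate with FC I credited = p[(1 − f) + f·r]. Loss = f·r·p.

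| p | f | Rate as written | Loss, r = 1 | Loss, r = 0.5 |
|---|---|---|---|---|
| 20% | 2% | 19.6% | 0.4 points | 0.2 points |
| 20% | 10% | 18.0% | 2.0 points | 1.0 point |
| 30% | 2% | 29.4% | 0.6 points | 0.3 points |
| 30% | 10% | 27.0% | 3.0 points | 1.5 points |

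Suppose there is no true difference, nobody in Group 1 is in FC I at baseline, and r = 1. The crude Group 1 versus Group 4 odds ratio is then:

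- f = 2%, p = 20%: (0.20/0.80) ÷ (0.196/0.804) = 1.03;
- f = 10%, p = 30%: (0.30/0.70) ÷ (0.27/0.73) = 1.16.

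**The case against.** The strongest reply concerns direction. A reader might infer that the definition alone tilts the Group 1 versus 4 and Group 1 versus 3 comparisons toward always-active treatment. The documents do not support that, for two reasons.

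- It needs parent-study entrants to have been FC II to IV. The parent eligibility criteria are not in these documents. The only support is the development indication in section 1, and the synopsis target population gives no class range.
- It needs the split baseline to apply to item 5. Section 8.4 says it does, but item 5 is silent and its neighbours point elsewhere. Item 2 and the Tier 2 analyses in 8.5.3 use change from LTE baseline, and the clock in 5(b) starts at the first LTE dose for every group.

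This part of the reply stands, so the direction has to be stated conditionally.

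The size can also be challenged. The FC I share is assumed, and FC I subjects must still gain at least 30 m, with no credit for an already long walk. They may have less room to do so, which makes r = 1 an upper case. The crude odds ratios are also not the planned estimate, because the logistic model adjusts for parent and LTE baseline REVEAL Lite 2 scores. Both points stand, although adjustment cannot restore a response that the definition rules out.

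Third, a reader might see a contradiction with item 3. It is not one: item 3 credits stability in any class, even FC IV, and an improvement composite may be stricter. But strictness does not explain crediting stable FC II and not stable FC I.

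Finally, the study's primary objective is safety, and the documents tie no power calculation or decision rule to this endpoint. That limits the consequence but does not remove the error.

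**Conclusion.** The rule is wrong as written at subject level. Anyone in FC I at the reference baseline is a fixed non-responder in 5(a) and can never have the event in 5(b), and no other section repairs this. The conclusion rests on reading maintenance as maintenance from baseline. Without that reference, a subject who slipped from FC I to FC II and stayed there might be credited, which would be perverse.

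The group-level effect is conditional. Under 8.4, with parent entry in FC II to IV, it falls on Groups 3 and 4 and favours Group 1. Under LTE baseline for all groups it reaches Groups 1 and 2 as well and could reverse. Its size is unknown and probably small: for the affected ex-placebo groups, at most about 0.4 to 3 percentage points over the assumed ranges, and half that if FC I subjects respond half as often.

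**What to change.** In the synopsis, 2.2, 6.6.6 and 8.5.2(5), change the component to: WHO FC improvement, or maintenance of WHO FC I or II. The derivation should make clear that a subject in FC I at baseline must still be in FC I at the visit. In 8.5.2(5), state that the reference baseline for the components is the one defined in 8.4.

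The cost is one phrase in four places and one added sentence. With the baseline fixed, results for subjects in FC II to IV at baseline do not change, and patient management is unaffected. The one downside is that the wording may then differ from the parent study's composite, which is not in these documents. Check it against that definition before adopting it; if nobody was in FC I at parent baseline, the change would make no difference there.
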